9.4 Compensation for injury	26
10 ADMINISTRATIVE ASPECTS, MONITORING AND PUBLICATION	27
10.1 Handling and storage of data and documents	27
10.2 Amendments.....	27
10.3 Annual progress report.....	27
10.4 End of study report.....	27
10.5 Public disclosure and publication policy	27
11. REFERENCES.....	28
12. APPENDIX	29

LIST OF ABBREVIATIONS AND RELEVANT DEFINITIONS

ABR	ABR form, General Assessment and Registration form, is the application form that is required for submission to the accredited Ethics Committee (In Dutch, ABR = Algemene Beoordeling en Registratie)
AE	Adverse Event
AR	Adverse Reaction
CA	Competent Authority
CCMO	Central Committee on Research Involving Human Subjects; in Dutch: Centrale Commissie Mensgebonden Onderzoek
CV	Curriculum Vitae
DSMB	Data Safety Monitoring Board
EU	European Union
EudraCT	European drug regulatory affairs Clinical Trials
GCP	Good Clinical Practice
IB	Investigator's Brochure
IC	Informed Consent
IMP	Investigational Medicinal Product
IMPD	Investigational Medicinal Product Dossier
METC	Medical research ethics committee (MREC); in Dutch: medisch ethische toetsing commissie (METC)
(S)AE	(Serious) Adverse Event
SPC	Summary of Product Characteristics (in Dutch: officiële productinformatie IB1-tekst)
Sponsor	The sponsor is the party that commissions the organisation or performance of the research, for example a pharmaceutical company, academic hospital, scientific organisation or investigator. A party that provides funding for a study but does not commission it is not regarded as the sponsor, but referred to as a subsidising party.
SUSAR	Suspected Unexpected Serious Adverse Reaction
Wbp	Personal Data Protection Act (in Dutch: Wet Bescherming Persoonsgegevens)
WMO	Medical Research Involving Human Subjects Act (in Dutch: Wet Medisch-wetenschappelijk Onderzoek met Mensen)

SUMMARY

Rationale: There is no consensus about the optimal treatment of displaced intra-articular distal radius fractures in elderly patients. To ensure optimal functional outcome there is a tendency to operate. However, there is no evidence that supports the surgical treatment of patients aged 65 years or older and in the absence of clinical trials it stays unclear how elderly patients with intra-articular fractures should be treated.

Objective: Assessing the *clinical outcome* of open reduction and internal fixation compared with non-operative treatment for elderly patients with displaced intra-articular distal radius fractures.

Study design: Multi-center randomized controlled trial with a non-inferiority design and an economic evaluation alongside.

Study population: All consecutive patients aged 65 years and older with displaced intra-articular (AO Type C) distal radius fractures, with non-acceptable fracture characteristics within 3 weeks following trauma.

Intervention: Open reduction and internal fixation (intervention group) and plaster immobilization (control group).

Main study parameters: The primary outcome will be evaluated after 1 year with the Patient-Rated Wrist Evaluation score (PRWE).

Secondary outcomes comprise other patient reported outcome measures (PROMs) including the Disability of the Arm, Shoulder and Hand (DASH) and Quality of life (EQ-5D). Further outcome measurements comprise a costs evaluation questionnaire, range of motion (ROM), grip strength, radiographic parameters, Pain Catastrophizing Scale (PCS) and Complications.

Nature and extent of the burden: The treatment that study participants receive is a component of standard treatment of care. Prior research suggests there is no difference in long-term function between both treatment groups. Currently the choice of treatment is based on the preference of the surgeon, the complexity of the fracture and the national guideline for the treatment of radius fractures.

Post-operatively or after cast therapy patients will be seen 1 week, 3 weeks, 6 weeks, 3 months, 6 months and 12 months after trauma. The visits are standard care for patients following a fracture of the distal radius. After 6, 9 and 12 months depending on the treating physician's and/or patients' preference they can visit the hospital or can be visited at home. During these visits patients will be asked about complaints or complications, which is also part of regular care.

At baseline, and after 6 weeks, 3 months, 6 months, 9 months and 12 months patients will be asked to fill out 4 questionnaires mentioned earlier. These questionnaires can be filled out at home, online, or in the hospital prior to their visit and will take approximately 30 minutes for each of the 6 follow-up moments.

DART - Surgery vs. Casting for Displaced Articular Radius Fractures in Elderly

Prior to some visits, X-rays of the wrist will be made. The radiographs that are made during this study are all part of standard care.

In total study participants will spend 210 minutes to this study. This includes informed consent and the questionnaires.

The risks of this study are comparable to risks involved with standard treatment. This comprises the standard risk for undergoing a surgical procedure, including risks related to anesthesia, neurovascular damage and post-operative wound infection. The risks of closed reduction and plaster immobilization include stiffness, redislocation, malunion, loss of function and complex regional pain syndrome.

Possible complications will be treated according to standard protocol.

1. INTRODUCTION AND RATIONALE

INTRODUCTION AND RATIONALE:

Distal radius fractures are the second most common fractures in the elderly population and cause high health-care costs per patient, especially in elderly patients^{1,2}. As a result of the high incidence and high costs per patient, distal radius fractures account for a substantial part of total health care costs^{3,4}. In the coming decades this will further increase by a progressively aging population⁵.

The treatment of distal radius fractures can be either non-operative or operative. The non-operative treatment consists of closed reduction followed by casting. The most commonly used operative procedures are external fixation, K-wire stabilization and open reduction and internal fixation (ORIF). Especially ORIF has gained in popularity. In the last decade it has become the most popular method of surgical treatment⁶. There is no evidence however that supports the superiority of this operative treatment over non-operative treatment but still the number of these surgical procedures is increasing^{6,7}.

Distal radius fractures can be either extra- or intra-articular. Very few extra-articular fractures are treated surgically. Intra-articular fractures however are more likely to be treated surgically, because articular incongruity resulting from a fracture is believed to cause arthritis⁸. About half of the distal radius fractures are intra-articular^{9,10}.

Patients with an intra-articular distal radius fracture who are treated surgically can rehabilitate faster because of surgical stabilization of the fracture. However, patients who are treated surgically are more likely to suffer from complications. Also surgical treatment is expensive and the long-term outcome does not seem to differ with that of non-operative treatment in terms of patient reported outcome measurements^{11,12}.

Non-operative treatment by closed reduction and casting is safe, simple, inexpensive and non-invasive¹³. A disadvantage is that up till 60% of fractures redislocate. However, several studies suggest elderly patients who are treated non-operatively have satisfactory function of their wrist even despite of malunion and poor radiographic outcome^{14,15}. Another downside to non-operative treatment is that it requires a longer duration of immobilization.

There is no evidence to support operative over non-operative treatment for elderly patients with a displaced intra-articular distal radius fracture. In the absence of powerful clinical trials it remains unclear how patients aged over 65 with displaced intra-articular fractures should be treated⁷.

HEALTH CARE EFFICIENCY PROBLEM

Guidelines are inconclusive about the recommended choice of treatment for elderly patients with an intra-articular distal radius fracture^{16,17}. Despite of a lack of evidence, open reduction and internal fixation (ORIF) is gaining in popularity. About one-fourth of elderly patients with an intra-articular fracture are now treated operatively. It is hypothesized that compared to the non-operative treatment this surgical procedure does not actually lead to better results⁶.

Moreover, there may even be more disadvantages to surgical treatments such as an increased risk of complications, and higher healthcare costs^{7,13}.

USUAL/STANDARD CARE

The choice of treatment is prone to surgeon preference, which results in a high variance in practice. The absence of a guideline recommendation makes it unclear what can be called the "standard" treatment. Because three-fourth of patients is treated non-operatively this could be regarded as the "standard" treatment. However in this study surgery is chosen as the "standard" because this is the treatment that will be challenged

2. OBJECTIVES

OBJECTIVE: Assessing the *clinical outcome* of open reduction and internal fixation compared with non-operative treatment for elderly patients with intra-articular distal radius fractures.

HYPOTHESIS: Cast treatment is not inferior to surgical open reduction and internal fixation in term of patient reported outcome measures.

3. STUDY DESIGN

DESIGN

A multi-center randomized controlled trial with a non-inferiority design and an economic evaluation alongside.

The article will be written according to CONSORT guidelines (Consolidated Standards of Reporting Trials).

4. STUDY POPULATION

POPULATION

Patients aged 65 years or older with displaced completely intra-articular distal radius fractures (AO type C).

Inclusion criteria:

- ≥65 years at time of trauma
- Intra-articular distal radius fracture (AO type C*)
- One or more of the following fracture characteristics within 3 weeks post-trauma (including secondary dislocation):
 - ≤15° inclination
 - ≤5 mm radial length
 - >15° dorsal tilt
 - >20° volar tilt
 - intra-articular gap or step-off >2 mm
(This will be measured by 1 researcher)
- < 3 weeks post trauma
- Living independent at home (e.g. not in a retirement home)
- Fit for surgery
- Mentally competent
The patient must be able to fully understand the consequences of participation. This includes that the patient must be aware of the burden that the research project provides, the possible complications in both treatment arms and the possibility to not participate in the trial. Furthermore he or she must be able to fill out the questionnaires.
- Dutch fluency and literacy
- Informed consent

Exclusion criteria:

- Open fractures
- Neurovascular damage
- Multiple-trauma patients (ISS >16)
- Other fractures in the injured extremity other than ulnar styloid process fractures
- Simultaneous fracture of the contralateral forearm
- Previous fracture of the ipsilateral radius resulting in a malunion or an impaired function

*Classifications will be made based on posterior-anterior (PA) and lateral radiographs. When in doubt about articular involvement CT images can be acquired by the treating physician.

SAMPLE SIZE CALCULATION

The study will be a non-inferiority study. Sample size calculation is based on a power of 90%, an alpha of 0.025, a standard deviation of 23 points and a minimal important change of 14 points based on the PRWE^{12,25} as primary outcome measure after 1 year. In addition we take into account that outcome data will be correlated within 19 participating centers with an ICC of 0.1. We calculated that with 20% loss to follow-up after 12 months, 57 patients are needed per group in this non-inferiority trial. This means 114 patients need to be included.

FEASIBILITY

The subject of this study concerns an important question in current orthopedic practice. The subject is the result of a survey that was carried out by the Dutch Orthopedic Association (NOV) about knowledge gaps in the field of orthopedic surgery. The survey was held in 2013 in cooperation with the 'Stimuleer Effectieve Elimineer Niet Effectieve Zorg' (SEENEZ) project.

This study is feasible due to the high incidence of distal radius fractures in the elderly. In the Netherlands every year 15.000 people aged 65 or older suffer a distal radius fracture (Declaration Data Hospital Care Vektis). Half of these fractures are intra-articular¹⁰. About 80% of the intra-articular fractures are type C fractures which are the types we plan to study⁹. In our project group of at least 6 participating clinics each year 450 elderly patients with type C fractures will be treated. Assuming a participation of 25% we therefore are confident to include the required number of patients in this study. We expect that inclusion will be completed within 18 months.

Because a collective of orthopedic surgeons has chosen this subject, the conduction of this research will be widely supported. This broad support facilitates the multicenter collaboration that is needed to enroll a sufficient number of study participants. For this study, we will use the collaboration between orthopedic departments (Orthopedic Consortium Mid-West Netherlands), which was started by the ESCAPE study (ZonMw project number: 837002009). There will be collaboration with the trauma departments of these hospitals because of the multidisciplinary nature of the study. This collaboration will be facilitated by collaboration with the trauma surgery department that is conducting the VIPER trial that focuses on extra-articular distal radius fractures. This trauma surgical community has a strong and successful reputation in conducting multicenter randomized clinical trials (e.g. ZonMw project numbers: 171102023, 171102023, 837001407).

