6.5 Replacement of individual subjects after withdrawal

The number of patients who withdraw from the trial will not be replaced unless the number of anticipated loss to follow-up patients is exceeded. If informed consent is withdrawn, data collected so far will be used unless the patient explicitly asks to be removed from the study database. If patients cross over from one group to the other, patients will be asked to be

followed up to comply with the intention-to-treat principle so as to obtain a complete database of consecutive patients and to avoid attrition bias.

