8. STATISTICAL ANALYSIS

To answer our primary research question, whether the change in PRWE differs between treatment groups at 1 year after trauma, we will calculate the intervention effect using a mixed model, with intervention group and baseline PRWE as fixed factors and clusters (random factors) for repeated observations within patients and patients within hospitals (the latter only if a significant random intercept of hospital is observed).. Both crude and adjusted intervention effects will be calculated on an intention-to-treat and as-treated basis.

To further investigate the intervention effect over time, we will add time as fixed effect as well as an interaction between time and intervention group. , The secondary outcome variables will be analyzed in a similar way.

In additional analyses, we will investigate confounding and effect modification of several patient and fracture characteristics.

The primary outcome will be tested for non-inferiority with respect to the predefined threshold of 14 points on the PRWE, with a one-sided 97.5% confidence interval. For superiority analyses, a two-tailed value of $p < 0.05$ is considered to be significant.

COST EFFECTIVENESS ANALYSIS (CEA)

General considerations

Within this project, we will perform an economic evaluation that is in accordance with the most recent guidelines of “The National Health Care Institute”¹⁸.

Cost analysis

An economic evaluation will be performed from a societal as well as a healthcare perspective¹⁹. When the societal perspective is applied, all costs and consequences relevant to the intervention will be taken into account irrespective of who pays or benefits, whereas solely those accruing to the healthcare sector will be taken into account when the healthcare perspective is applied²⁰. Intervention costs will be estimated using a micro-costing approach¹⁸. Cost questionnaires will be administered on a 3-monthly basis to collect data on healthcare utilization, the use of informal care, and unpaid productivity losses.

Patient outcome analysis

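### The 57 patients per group is the plain formula result before any loss to follow-up or ICC; with the assumed 20% loss, the stated inputs give about 82-83% power (at most about 86-87%), not 90%

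*Protocol*

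**What the plan says.** The hypothesis in Protocol section 2 is that "Cast treatment is not inferior to surgical open reduction and internal fixation in term of patient reported outcome measures". The sample size paragraph in section 4 gives its inputs: "Sample size calculation is based on a power of 90%, an alpha of 0.025, a standard deviation of 23 points", with a minimal important change of 14 points on the Patient-Rated Wrist Evaluation (PRWE) at one year. It adds that "outcome data will be correlated within 19 participating centers with an ICC of 0.1", and concludes: "We calculated that with 20% loss to follow-up after 12 months, 57 patients are needed per group in this non-inferiority trial". The total to be included is given as 114.

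Section 8 repeats the 14 points as the non-inferiority threshold, to be tested "with a one-sided 97.5% confidence interval", so the alpha of 0.025 is one-sided. Section 6.2 randomises individual patients, stratified by age only. Section 8 plans a mixed model with baseline PRWE and repeated observations within patients. A hospital random intercept is kept only if it is significant.

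**The concern.** The paragraph presents 57 per group as an enrolment figure that already allows for 20% loss and for correlation within centres, and attaches 90% power to it. Yet 57 is what the simplest two-group formula returns with neither allowance made.

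If so, the power for the primary comparison is overstated on the plan's own inputs. An ethics committee or a reader of the results would take the chance of missing non-inferiority, when the treatments are truly equal, to be 10%. On the loss assumed in the plan it would be about 17-18%, or about 13-14% with the most favourable treatment of the ICC.

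**Working it through.** **Inputs.** From Protocol section 4: power 90%, alpha 0.025, SD 23, difference 14, ICC 0.1, loss 20%, 57 per group. From section 8: the test is one-sided and the margin is 14. Assumed: a true difference of 0, since no other value is given.

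**Step 1: reproduce the plan's figure.**
n per group = 2 × (z0.975 + z0.90)² × SD² / margin² = 2 × (1.960 + 1.2816)² × 23² / 14² = 56.72, rounded up to 57.
This matches the stated figure exactly, with no loss and no ICC. (The t-based version gives 58.)

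**Step 2: add what the text says is included.**

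- 20% loss only: 56.72 / 0.8 = 70.9, so 71 per group (72 if 57 is rounded first).
- 20% loss, with the ICC credited as removal of between-centre variance (factor 1 − 0.1 = 0.9): 56.72 × 0.9 = 51.05, and 51.05 / 0.8 = 63.8, so 64 per group.
- Inflating by 1.2 instead of dividing by 0.8: 68.1 without the ICC credit and 61.3 with it, so 69 and 62.

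None of these gives 57. A one-sided alpha of 0.05 comes close (46.23 / 0.8 = 57.8, so 58), but it contradicts the stated 0.025 and the 97.5% interval, and it still leaves out the ICC.

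**Step 3: power of 114 enrolled after 20% loss.**
Analysable per group: 57 × 0.8 = 45.6.

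- Loss only: SE = 23 × √(2/45.6) = 4.817; power = Φ(14/4.817 − 1.960) = 82.8%. It is 82.3% at 45 and 83.1% at 46 per group; the noncentral t gives 82.0% at 45.6.
- With the 0.9 factor: SE = 4.817 × √0.9 = 4.570; power = Φ(14/4.570 − 1.960) = 86.5%. It is 86.1% at 45 and 86.8% at 46; the noncentral t gives 85.8% at 45.6.

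**Step 4: what would restore 90% at 45.6 per group.**
Baseline adjustment multiplies the variance by 1 − ρ².

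- Without ICC credit: 1 − ρ² = 45.6 / 56.72, so ρ = 0.44.
- With the 0.9 factor: 1 − ρ² = 45.6 / 51.05, so ρ = 0.33.

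The protocol gives no correlation of this kind.

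**The case against.** The strongest reply is that these powers describe a simple comparison of 12-month scores among completers, whereas section 8 plans a mixed model with baseline PRWE and repeated follow-ups, in which patients lost by 12 months still contribute earlier scores. That stands as far as it goes. A baseline correlation of 0.33 to 0.44 would restore 90%. A reader might therefore infer too much from the figures above, namely that the trial as analysed is certain to have less than 90% power. The document does not support that: power under the planned model is unknown without the correlation. Nor does the reply rescue the sentence in section 4, which lists its inputs, names no such correlation, and arrives at exactly the unadjusted result.

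Three other strong readings are tempting and should not be drawn.

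- *A cluster design effect.* One might inflate for the ICC as if centres were randomised, and find a much larger shortfall. Patients are randomised, not centres, so that inflation does not fit this design. With centre in the model the ICC helps if anything. The 0.9 factor is a best case, because randomisation is not stratified by centre and the hospital term is kept only if significant.
- *A conflict in centre counts.* The feasibility text says "In our project group of at least 6 participating clinics each year 450 elderly patients with type C fractures will be treated". That is a minimum and is compatible with 19 centres.
- *A shortfall that is bound to occur.* Section 6.5 says that withdrawals "will not be replaced unless the number of anticipated loss to follow-up patients is exceeded". This means the anticipated loss would not be made up. It does not show that 20% will be lost. At 10% loss, 51.3 per group remain, and power is 86.9%, or 90.1% with the 0.9 factor.

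It is also fair to say that the margin, the type I error and the analysis are untouched, and that power stays above 80% on both readings.

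**Conclusion.** The sample size statement is wrong as written. The inputs in section 4 yield 57 analysable patients per group, and the text presents that number as already covering 20% loss and an ICC of 0.1. It covers neither, and no use of the stated inputs that includes the loss returns 57.

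If the anticipated 20% is lost, power on the stated inputs is about 82-83%, or at most about 86-87% with the ICC credited as a variance reduction. The enrolment that matches the text would be 71 or 64 per group. These figures rest on a true difference of zero, equal group sizes, and an analysis with no gain from baseline or earlier visits. A stated correlation, or a stated true difference in favour of casting, would change them; the protocol gives neither.

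**What to change.** Correct the sample size paragraph in Protocol section 4:

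- State that 57 per group is the number of analysable patients for 90% power.
- Give the power of 114 enrolled after 20% loss as about 82-83%, or up to about 86-87% if the ICC is credited as removal of between-centre variance.
- Say how the ICC of 0.1 enters the calculation.
- State the assumed true difference.
- If 57 rests on a variance reduction from baseline or repeated measures, give the assumed correlation and the resulting power.

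This costs only wording and needs no additional patients. The price is a stated power that looks less favourable, unless a correlation can be justified that supports 90%.

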5. TREATMENT OF SUBJECTS

ALL GROUPS

Study procedures:

Patients with an intra-articular fracture (AO type C) who meet the above mentioned inclusion criteria are eligible for the study. The surgeon on duty or the emergency physician is responsible for this initial screening.

In each eligible patient the surgeon on duty or the emergency physician will initially attempt to reduce the fracture after which the patient receives a temporary below-elbow forearm cast. For this, participating hospitals may use their preferred technique. Also they may follow their local protocol for anesthetics.

Preferably, eligible patients will receive information about the study at the emergency department.

One week after trauma they will be seen at the outpatient clinic. They can sign an informed consent form if they agree to participate up to 3 weeks after trauma.

Upon obtaining informed consent, patients will be randomized into either the surgical intervention group (open reduction and internal fixation) or the control group (closed reduction and plaster immobilization). For both treatment arms, participating hospitals may use their preferred technique. Also they may follow their local protocol for anesthetics, duration of cast treatment and vitamine C prescription. These data will be collected to correct for during data analysis.

In order to avoid any imbalance between treatment groups, patients will be randomized in 2 strata using a block randomization. Two strata according to age: 65-75 and 75 and older.

At baseline characteristics will be collected such as sex, side, dominant hand, trauma mechanism and the frailty questionnaire (frailty score <1 week after trauma).

Post-treatment patients will be seen at the outpatient clinic according to the regular protocol. These visits are also used for the follow-up assessments. Data is collected at 1 week, 3 weeks, 6 weeks, 3 months, 6 months, and 12 months. After 6, 9 and 12 months depending on the treating physician's and/or patients' preference they can visit the hospital or can be visited at home.

The Patient-Rated Wrist Evaluation score (PRWE), the Disability of the Arm, Hand and Shoulder (DASH), Quality of life (EQ-5D) and Costs evaluation questionnaire) will be obtained online or by hardcopy at baseline, 6 weeks, 3 months, 6 months, 9 months and 12 months. .

DART - Surgery vs. Casting for Displaced Articular Radius Fractures in Elderly

An x-ray of the wrist will be obtained prior to visits according to standard protocol, including one bilateral X-ray. Range of motion and grip strength will be tested at 6 weeks, 3 months, 6 months and 12 months.

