1. INTERVENTION GROUP

A CT-scan may be acquired for patients in the intervention group as part of the pre-operative planning. Patients will undergo surgical open reduction and internal fixation (ORIF) with a volar locking plate and/or dorsal plate. An additional cast may be applied for a maximum of 2 weeks post-surgery for wound protection. Patients are instructed to use their wrist as pain allows for. Patients are referred for physical therapy at the discretion of their treating physician or according to local protocol.

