2. CONTROL GROUP

[figure not shown]
The conservatively treated patient group receives a permanent circular cast between 1 and 2 weeks after trauma. The total duration of cast treatment may vary between 4-6 weeks according to local protocol. Vitamin C 500mg may be prescribed to prevent complex regional pain syndrome (CRPS) according to local protocols. Patients are referred for physical therapy according to local protocol or at the discretion of their treating physician. Unless there is a strong clinical indication, it is not possible for patients in the conservative arm to crossover to the operative group during the period of cast treatment (worsening of radiographic fracture characteristics or pain complaints during cast treatment are not criteria for crossover).

Use of co-intervention (if applicable)

Not applicable

Escape medication (if applicable)

Not applicable

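### Section 5 says cast duration and technique will be corrected for in the analysis, but these are parts of the allocated treatments and do not belong in the treatment-effect model

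*Protocol*

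**What the plan says.** Section 5 (All groups, Study procedures) leaves several treatment choices to the hospital after randomisation: "For both treatment arms, participating hospitals may use their preferred technique". It continues: "Also they may follow their local protocol for anesthetics, duration of cast treatment and vitamine C prescription". The next sentence gives the purpose of recording them: "These data will be collected to correct for during data analysis".

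The arm descriptions in Section 5 show how far these choices depend on the arm:

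- **Cast duration, surgery arm:** "An additional cast may be applied for a maximum of 2 weeks post-surgery for wound protection".
- **Cast duration, control arm:** "The total duration of cast treatment may vary between 4-6 weeks according to local protocol".
- **Technique, surgery arm:** "surgical open reduction and internal fixation (ORIF) with a volar locking plate and/or dorsal plate".
- **Vitamin C, control arm:** "Vitamin C 500mg may be prescribed to prevent complex regional pain syndrome (CRPS) according to local protocols". The general paragraph quoted above, however, allows it in both arms.

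Section 8 gives a primary mixed model with treatment arm and baseline PRWE as fixed factors. It then says: "Both crude and adjusted intervention effects will be calculated on an intention-to-treat and as-treated basis". It does not list the covariates of the adjusted effect, and does not say whether the crude or the adjusted effect is compared with the 14-point margin.

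**The concern.** Randomisation already protects the comparison from confounding by anything that happens after it. Cast duration and plating technique are not background differences between patients; they are part of what each arm consists of. Holding cast duration constant asks how the arms would compare if patients were immobilised equally long. That is not the hypothesis in Section 2, which concerns cast treatment against surgical fixation as given.

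Two things are at stake. The first is bias: if longer immobilisation is the reason cast patients do worse, the correction removes that deficit from the estimate, which is the dangerous direction in a non-inferiority trial. Conditioning on a variable measured after randomisation can also add bias of its own, for instance if a poor course leads to both a longer cast and a worse score. The second is precision: cast duration is strongly correlated with arm, so the corrected effect has a wider interval.

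**Working it through.** **Inputs from the protocol.** SD 23, margin 14, one-sided alpha 0.025, power 90%, 57 per group (Section 4, Sample size calculation). Cast duration 4-6 weeks in total in the control arm, and at most 2 weeks after surgery in the other arm (Section 5). All patients receive a temporary cast at first reduction, are seen at 1 week, and may consent up to 3 weeks after trauma (Section 5).

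**Assumed.** The distributions of cast duration within these ranges; equal arms; residual SD still 23 after correction; no true difference for the power figures.

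**The plan's own figure.** 2 × (23 × (1.960 + 1.282) / 14)² = 56.7, so 57 per group. This is the number before any allowance for loss or clustering, which is a separate matter; here it only supplies n.

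**Uncorrected effect.** SE = 23 × √(2/57) = 4.31. Half-width = 1.96 × 4.31 = 8.4 points. Power = Φ(14/4.31 − 1.96) = 90%.

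**Corrected for cast duration.** With equal arms, the between-arm variance of duration is B = (difference in means)²/4, and W is the average within-arm variance. The variance inflation factor is VIF = 1/(1 − R²) = 1 + B/W. The SE and half-width are multiplied by √VIF.

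| Assumed weeks in cast: control vs surgery | B | W | VIF | SE | Half-width | Power |
|---|---|---|---|---|---|---|
| Total time: uniform 4-6 vs uniform 1-5 | 1 | 0.833 | 2.2 | 6.39 | 12.5 | 59% |
| Total time: uniform 4-6 vs (1-3 before + 0-2 after surgery) | 1 | 0.5 | 3.0 | 7.46 | 14.6 | 47% |
| Total time: uniform 4-6 vs uniform 1-4 | 1.5625 | 0.542 | 3.9 | 8.49 | 16.6 | 38% |
| Ranges as stated: 4, 5 or 6 vs 0, 1 or 2, equally likely | 4 | 0.667 | 7.0 | 11.4 | 22.3 | 23% |
| Ranges as stated: uniform 4-6 vs uniform 0-2 | 4 | 0.333 | 13 | 15.5 | 30.4 | 15% |
| Ranges as stated: uniform 4-6 vs all at 2 | 2.25 | 0.167 | 14.5 | 16.4 | 32.1 | 13% |

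The last three rows set a total duration in one arm against a post-surgery duration in the other. The first three count casting before surgery too; a surgical patient can then reach 3 + 2 = 5 weeks, which overlaps the control range. If 20% are lost (45.6 per arm analysed), every half-width grows by √(57/45.6) = 1.12, and the uncorrected one becomes 9.4.

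**Bias.** Suppose the outcome depends on arm only through duration: score = β × duration + error. The uncorrected arm effect is then β × (difference in mean duration), while the coefficient of arm given duration is zero in expectation, whichever distribution holds. A simulation (57 per arm, 4,000 runs, uniform 4-6 vs 0-2 weeks) agrees:

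| True difference, all through duration | Mean uncorrected estimate | Mean corrected estimate |
|---|---|---|
| 14 | 13.9 | 0.4 |
| 10 | 10.0 | 0.2 |
| 6 | 5.9 | −0.3 |

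The corrected means are zero within simulation error (SD about 15.5; 15.5/√4000 = 0.25). If only a share of the difference acts through duration, that share is what the correction removes.

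**Technique.** Plate type exists only in the surgery arm. If dorsal plating is a covariate, coded zero for every cast patient, the arm coefficient compares cast with volar-plated patients only. The contrast changes with the reference category chosen.

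**Vitamin C.** Equal use in both arms: VIF 1.0, no loss. 80% vs 20%: R² = 0.09/0.25 = 0.36, VIF 1.56, half-width 10.5. 50% vs 0%: R² = 0.0625/0.1875 = 0.33, VIF 1.50, half-width 10.3.

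**The case against.** The strongest reply is that the sentence stands in a treatment section and fixes no model. Section 8 names only arm and baseline PRWE as fixed factors, keeps a crude effect, and mentions confounding only for patient and fracture characteristics in additional analyses. The practices listed vary by hospital, so the sentence may aim at between-hospital differences, and the covariate list may sit in a statistical analysis plan that is not shown. Much of this stands: an uncorrected estimate survives. But the sentence states an intention to correct, it is the only place that names treatment variables for that purpose, and nothing in Section 8 keeps them out of the adjusted effect.

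Several stronger readings go beyond the text:

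- A reader might infer that the adjusted effect is what will be tested against 14 points. Section 8 does not say so; it leaves the choice open.
- A reader might take the half-width of 30 points as the expected harm, or conclude that no patient in one arm could share a cast time with the other. Both ignore casting before surgery.
- A reader might say the corrected half-width always exceeds the margin. It does not: one plausible distribution gives 12.5.
- Vitamin C might seem confined to the cast arm, where its dose is described. The general paragraph allows it in both arms by local protocol.
- Not all anaesthesia follows randomisation: the local protocol also covers the initial reduction, which comes before consent.
- Section 6.1.2 lists radiographic parameters and the Pain Catastrophizing Scale as explanatory variables. No text puts them in the treatment-effect model, so this point does not extend to them.

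**Conclusion.** The point holds for cast duration and arm-specific technique. Followed as written, Section 5 would yield an adjusted effect that does not estimate cast versus surgery and that loses, in expectation, any part of the difference acting through immobilisation. That bias does not depend on the assumed distribution of cast time; it depends on how much of the effect runs through duration, which the protocol does not give.

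The loss of precision is real but uncertain in size. Counting total cast time, VIF is about 2.2 to 3.9 and power falls from 90% to between about 59% and 38%. The larger losses in the table need the two stated ranges to be compared without counting casting before surgery.

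The primary question stays answerable through the model in Section 8. The defect is that the protocol announces an unsuitable correction and does not say which effect decides non-inferiority. For vitamin C, harm arises only if its use differs between arms.

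**What to change.** Three changes of wording:

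1. **Section 5.** Replace the sentence on correction with a statement that technique, anaesthetics, cast duration and vitamin C are recorded to describe the treatment delivered, are reported by arm or explored within arm, and are not covariates in the treatment-effect model.
2. **Section 8, adjusted effect.** Limit the covariates to variables recorded before allocation and already collected: baseline PRWE, age stratum, hospital, and fracture characteristics and frailty where recorded before allocation.
3. **Section 8, non-inferiority test.** State that the comparison with the 14-point margin uses the model without post-randomisation covariates.

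The cost is an amendment to the text, preferably before any outcome data are analysed. No data item, visit, sample size or treatment changes.
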